# 2.0 STUDY OBJECTIVES

**Primary Objective:** To determine the validity of a CPR for identifying patients with neck pain who are likely to benefit from cervical TJM. The investigators hypothesize that patients who are positive on the rule and receive TJM will achieve greater improvement in 1-week and 4-week disability and pain than patients who are negative on the rule and receive TJM plus exercise *and* compared to patients who are positive on the rule but receive an alternative NTM plus exercise program without TJM.

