Specific Aims: Primary Aim #1: To determine the validity of the clinical prediction rule for identifying patients with neck pain who are likely to benefit from C-TJM. Pain and Disability. The investigators will examine the primary aim with separate random intercept linear mixed models with treatment group (MTE vs. MoE), status on the CPR (positive or negative) and time (baseline, 1-week and 4weeks) as fixed effects. The dependent variables will be pain (NPRS) and disability (NDI score). The hypothesis of interest is the group \* CPR status \* time interaction. The primary dependent variables are the 1-week NPRS and NDI scores to mirror the follow-up used in Cleland and colleagues' study. The investigators will assess the NPRS and NDI scores after 4 weeks to determine whether a patient's status on the rule predicts outcome at a longer follow-up. The investigators will perform planned pairwise comparisons at each follow-up period by using the Bonferroni test of inequality. The investigators hypothesize that patients who are positive on the rule and receive TJM will achieve greater improvement in immediate (1-week) and 4-week pain and disability, than patients who are negative on the rule and receive TJM, and compared to patients who are positive on the rule but receive an alternative exercise program without TJM. Because the rule is believed to be specific to a TJM intervention, investigators hypothesize that outcomes among those receiving the MoE treatment would not differ on the basis of a patient's status on the rule.

Secondary Aim #1: To compare the long-term (6-month) pain and disability scores (clinical

outcomes) and healthcare utilization based on status on the clinical prediction rule and the treatment received. The investigators will examine this with random intercept linear mixed models with treatment group (MTE vs. MoE), status on the CPR (positive or negative), and time (baseline and 6-months) as fixed effects. The dependent variables will be pain (NPRS) and disability (NDI) scores. The investigators will perform planned pairwise comparisons at each follow-up period by using the Bonferroni test of inequality. The hypothesis of interest is the group \* status on CPR \* time interaction. The investigators hypothesize that patients who are positive on the rule and received TJM would experience greater improvement at 6-months than patients who are negative on the rule and received the MoE program without TJM.

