Sample Size and Power. The sample size calculation is based on the primary aim of the study. This aim looks at the change in NDI at a 1-week follow-up as the dependent variable. The investigators based sample size calculation on detecting a statistically significant difference between any of the 4 cells of

the study which include the patient's status on the rule (patients that meet the CPR and patients that do not meet the CPR) and group (MTE and MoE) by using the 1-week NDI score at an alpha-level of 0.05. To maximize statistical power, investigators will aim to include 4 equal group sizes based on the rule status (positive vs. negative) and treatment (MTE vs MoE). Based on previous research investigators expect a standard deviation of change scores on the NDI of 12 points. To detect a 10 point change in NDI at the 1-week follow up (effect size 0.80) with 90% power using a two-tailed hypothesis and assuming a 50% distribution of patients who do and do not meet the rule based on our randomized block design, 31 patients per cell are required. The investigators will recruit 140 subjects into the study to control for dropouts prior to the 1- and 4-week follow-up and possible distribution discrepancies between the classifications. This will require recruitment of approximately 12 subjects per month over a 12-month recruitment period.

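### The 90% power in Section 7.0 belongs to one unadjusted two-cell comparison, not to the interaction named as the hypothesis of interest or to the Bonferroni-adjusted comparisons

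*Combined protocol and SAP*

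**What the plan says.** In Section 7.0, the Sample Size and Power paragraph opens with "The sample size calculation is based on the primary aim of the study". It then defines its target as "detecting a statistically significant difference between any of the 4 cells" of the two-by-two layout (CPR status by treatment), using 1-week NDI at alpha 0.05. The inputs are an SD of 12 for NDI change and the following: "To detect a 10 point change in NDI at the 1-week follow up (effect size 0.80) with 90% power using a two-tailed hypothesis". The result is 31 per cell, or 124 in all. Recruitment is set at 140 (35 per cell) to allow for dropout and uneven classification.

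The analysis of Primary Aim #1, in the same section, describes a linear mixed model with treatment, CPR status and time (baseline, 1 week, 4 weeks). It says "The hypothesis of interest is the group" by CPR status by time interaction, and "The primary dependent variables are the 1-week NPRS and NDI scores". It also provides for "planned pairwise comparisons at each follow-up period by using the Bonferroni test of inequality". It gives the reason for testing the interaction: "the rule is believed to be specific to a TJM intervention, investigators hypothesize that outcomes among those receiving the MoE treatment would not differ" by CPR status.

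The primary objective in Section 2.0 is worded pairwise. CPR-positive patients given TJM should show "greater improvement in 1-week and 4-week disability and pain than patients who are negative on the rule and receive TJM plus exercise", and should also do better than CPR-positive patients in the comparison arm.

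**The concern.** The paragraph ties its 90% to the primary aim, so a reader will attach that figure to the test the plan puts first. That test is the interaction, for which no target size and no power appear anywhere. The pairwise comparisons are to be adjusted for multiplicity, but the calculation spends the full 0.05 on one of them.

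The interaction is what tells a rule specific to TJM from a general marker of good prognosis. A difference between CPR-positive and CPR-negative patients within the TJM arm cannot do that, because the same difference might appear in the other arm. If the trial has well under 90% power for the interaction, a non-significant result could be read as failed validation when the design was unlikely to settle the question.

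**Working it through.** **Inputs.** From Sample Size and Power in Section 7.0: difference 10 points, SD of change 12, two-sided alpha 0.05, power 90%, 31 per cell calculated and 35 per cell recruited (140/4). From Primary Aim #1: 1 week as the primary time point, and no CPR difference expected in the MoE arm. All powers below use the noncentral t distribution and are given for n = 31 / 35 completers per cell.

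**1. The plan's own figure.** For one comparison of two cells:

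n = 2(1.960 + 1.282)² / (10/12)² = 21.02 / 0.694 = 30.3, so 31 per cell.

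This reproduces the plan. Power is 89.8% / 93.0%. The 31 comes from 10/12 = 0.83. With the printed 0.80, the same formula gives 21.02 / 0.64 = 32.8, so 33.

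**2. The 1-week interaction.** This is a difference of two differences across four cells:

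- SE of a two-cell difference = 12√(2/n) = 3.05 / 2.87
- SE of the interaction = 12√(4/n) = 4.31 / 4.06, larger by √2, with 4n − 4 degrees of freedom

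The plan states no interaction size. If CPR status makes a 10-point difference under TJM and none under MoE, the interaction is 10 − 0 = 10 points. That value is an inference, so a range is shown.

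| True interaction at 1 week | Power, 31 per cell | Power, 35 per cell |
|---|---|---|
| 5 points | 21.0% | 23.2% |
| 10 points | 63.4% | 68.7% |
| 15 points | 93.2% | 95.6% |

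- Detectable with 90% power: 14.1 / 13.2 points
- Detectable with 80% power: 12.2 / 11.45 points
- 95% CI half-width: 8.5 / 8.0 points
- Reaching 90% for 10 points takes about 61–62 completers per cell, twice the stated 31

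**3. The full interaction over three time levels.** This test has 2 df, and its power depends on the 4-week effect and on the correlation between the 1-week and 4-week changes. Neither is given. Assuming 10 points at both times:

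| Assumed correlation | Power, 31 per cell | Power, 35 per cell |
|---|---|---|
| 0.3 | 72.8% | 78.2% |
| 0.5 | 66.1% | 71.8% |
| 0.7 | 60.3% | 66.0% |

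A random-intercept model implies 0.5: with variance 2σ² for each change from baseline and covariance σ² from the shared baseline, σ²/2σ² = 0.5.

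**4. The Bonferroni comparisons.** Two-cell test for 10 points at 0.05/k:

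| Comparisons (k) | Alpha | Power, 31 per cell | Power, 35 per cell |
|---|---|---|---|
| 1 | 0.05 | 89.8% | 93.0% |
| 2 | 0.025 | 83.4% | 88.1% |
| 6 (all pairs of four cells) | 0.0083 | 70.8% | 77.6% |

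**The case against.** The best defence is that the paragraph never claims 90% for the interaction. Straight after naming the primary aim it declares a difference between cells, and the objective in Section 2.0 is itself two between-cell comparisons. On that reading the trial is sized for its hypotheses. This stands in part: 31 per cell is right for the declared contrast, and that contrast has the form of the stated objective. It does not dispose of the point. Primary Aim #1 gives the leading role to the interaction and adjusts the pairwise tests, and the calculation reflects neither.

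Second, the 10-point interaction is not the investigators' figure. That is true, and across 5 to 15 points power runs from 21% to 96%. The 63–69% is conditional, though 10 points is what the plan's target and its expected null under MoE imply together.

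Third, the three-level interaction has 2 df, so the 1-week contrast is not literally the planned test. Also true, but 1 week is the named primary time point. With 10 points at both follow-ups the 2-df test gives 66–72% at the correlation the model implies, which leads to the same conclusion.

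Fourth, only two comparisons are hypothesised as differences, and with 2 comparisons and no dropout power is 88%, close to 90%. That is fair. The 71–78% applies only if all six pairs are in the family, and the plan does not say.

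Finally, the 0.80 label is a small slip: even 33 per cell is 132 in all, within the 140. It adds no weight to the main point.

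**Conclusion.** The concern holds. The calculation is sound for the contrast it declares, but its 90% is not the power of the tests planned for the primary aim. With the protocol's SD of 12 and 31 to 35 completers per cell, a true 10-point interaction at 1 week would be detected with 63–69% power, so it would be missed about one time in three. The adjusted pairwise comparisons fall below 90% even with no dropout: 83–88% for 2 comparisons and 71–78% for 6.

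The interaction figures rest on the inferred 10 points; the pairwise figures rest on an assumed number of comparisons, because the plan gives none. That no interaction power and no family size are stated depends on neither assumption. This should be fixed, but it does not invalidate the design.

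**What to change.** Keep N = 140 and the model. In Section 7.0:

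1. State that 31 per cell and 90% power apply to one unadjusted two-cell comparison of 1-week NDI change.
2. Add: *For an assumed treatment by CPR interaction of 10 NDI points at 1 week, power is 63% with 31 and 69% with 35 completers per cell; the interaction detectable with 90% power is 14.1 and 13.2 points respectively.* If the team has a different target interaction, it should state that one and the matching power.
3. State how many comparisons the Bonferroni adjustment covers and give the matching power (83–88% for 2, 71–78% for 6).
4. Correct the effect size from 0.80 to 0.83.
5. State that the 1-week interaction estimate will be reported with its 95% confidence interval, so that a non-significant result can be read against its precision.

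The cost is wording only, with no extra patients and no change of model. The stated power becomes less favourable, and the team must commit to a number of comparisons.

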# 8.0 DATA SECURITY & PRIVACY/CONFIDENTIALITY

The research material obtained from human subjects in this project will be in the form of electronic or hard copy data. It will include baseline demographic and history information such as gender, age, weight, height, occupation, and medical history information. It will also include clinical outcomes measure questionnaires (e.g., NDI, FABQ) and physical examination findings (e.g. cervical range of motion, finding from special tests).

#### **Identifiers:**

After the screening process but before the first study session, each participant will be assigned a numerical Participant ID code by researchers at each clinical location. A site coordinator at each clinical site will maintain the list linking patient contact information to this ID number. At the end of the study this link list will be destroyed.

# **Confidentiality:**

# Identifying information:

To de-identify HIPAA-protected data before transferring it to Baylor University investigators will remove all Protected Health Information (PHI) including name, phone number, medical record numbers, health plan beneficiary number, etc. that could potentially identify an individual. Only de-identified data using Participant ID will be transferred to the principal investigator at Baylor. The signed Informed Consent forms and contact information forms will not include the ID number, and the site coordinator will maintain the electronic copies of both the consent forms and the contact information forms in a locked file cabinet in his/her private office or within a password-protected file. Apart from any other access required by Baylor University or the IRB, only the responsible site coordinator will have access to the key.

Non-identifying data: During the data collection period, access to non-identifying data at Baylor University and each participating physical therapy clinic will be limited to the principal investigator and a co-investigator who is not involved in data collection or treatment. Once the link list connecting participant identities to the Participant ID has been destroyed at the end of the study, all files will be transferred to the principal investigator. The investigators do not expect to collect any sensitive information that would require reporting to state or local authorities.

Any other guidance issued by the IRB will be followed.

# Data capture, verification, and disposition:

All data collected during the study will use only the Participant ID number, and [name] will maintain all electronic and hard copy files of all data collected by her team during the duration of the project.

Any data collected in hard copy format (e.g., questionnaires), will be scored and passed along to [name] and [name](statistician) in a de-identified spreadsheet for data analysis. File transfer will be by either a password-protected shared Dropbox account or via encrypted email.

Files transferred to [name] and [name] will be maintained on a password-protected computer on the secure Baylor University network and accessed only by them or a research assistant.

Once the link list has been destroyed, all files will be transferred to [name], who will maintain these data in electronic format on a secure, password-protected Baylor server for a minimum of ten years after all manuscripts have been published and results disseminated.

# Sharing study results:

The only screening procedure involved in the study is a physical exam by a licensed physical therapist. If the exam results in an unanticipated finding, the physical therapist will share that information with the participant and refer the participant back to his/her primary care provider for follow-up.

Participants will be given a verbal summary of their general examination results at the end of their first study session. However, the clinical utility of the details of the examination findings will not be fully understood until analysis has been completed. The investigators, therefore, do not plan to formally share the examination findings with either the participant or their primary care provider.

# 9.0 DATA & SAFETY MONITORING

Participant safety is of utmost importance. Although risks are minimal, participants will be appropriately monitored until the end of the study for the occurrence of adverse events. For any adverse experience reported during the study, the nature, onset, duration, intensity, and remedial action taken will be recorded. The PI will oversee the data and safety monitoring process. Any unexpected adverse event will be reported to the IRB, sponsor, and the participant's primary care provider. If unexpected adverse events occur, the IRB, sponsor and research team will make collaborative recommendations concerning individual participant continuation, continuation of the study, termination of the study, or other modifications of the trial based on the observed adverse effects under study.

In the event of a confidentiality breach, researchers will immediately report to the IRB, providing detailed information about the nature, extent, and impact of the breach. For any protocol

deviations, researchers will promptly report to the IRB, detailing the occurrence, reasons, and corrective actions taken. In both cases, researchers will maintain comprehensive documentation, including all communications and actions taken. The principal investigator will keep secure, detailed records of all study activities, deviations, and breaches, adhering to institutional policies and regulations for record retention. The investigators understand that the IRB, in collaboration with relevant offices, will determine necessary notifications to participants, regulatory agencies, and sponsors, and may require protocol amendments based on the reported incidents. The investigators commit to full cooperation with these processes to ensure the integrity of the study and the protection of participants.

APPENDIX A: NECK DISABILITY INDEX (NDI)

#### 4. Neck Disability Index

Name:

Date:\_ mm dd year

This questionnaire has been designed to give your therapist information as to how your neck pain has affected you in your everyday life activities. Please answer each section; marking only the ONE box which best describes your status today.

#### Section 1— Pain Intensity

- □ I have no pain at the moment.
- The pain is very mild at the moment.
- The pain is moderate at the moment.
- The pain is fairly severe at the moment.
- The pain is very severe at the moment.
- □ The pain is the worst imaginable at the moment.

#### Section 2-Personal Care (Washing, dressing, etc.)

- I can look after myself normally without causing extra pain.
   I can look after myself normally but it causes me extra
- pain.
- Let it is painful to look after myself and I am slow and careful.
- I need some help but manage most of my personal care.
- □ I need help every day in most aspects of self-care.
- I do not get dressed, wash with difficulty and stay in bed.

#### Section 3-Lifting

- I can lift heavy weights without extra pain.
- I can lift heavy weights but it causes extra pain.
- Pain prevents me from lifting heavy weights off the floor, but I can manage if they are conveniently positioned, for example on a table.
- Pain prevents me from lifting heavy weights but I can manage light to medium weights if they are conveniently positioned.
- I can lift only very light weights.
- I cannot lift or carry anything at all.

#### Section 4- Reading

- I can read as much as I want with no pain in my neck.
- I can read as much as I want to with slight pain in my neck.
- I can read as much as I want with moderate pain in my neck.
- I can't read as much as I want because of moderate pain in my neck.
- □ I can hardly read at all because of severe pain in my neck.
- I cannot read at all.

#### Section 5— Headache

- L l have no headache at all.
- □ I have slight headaches that come infrequently.
- I have moderate headaches that come infrequently.
- □ I have moderate headaches that come frequently.
- I have severe headaches that come frequently.
- I have headaches almost all the time.

#### Section 6--- Concentration

- □ I can concentrate fully when I want to with no difficulty.
- Lean concentrate fully when I want to with slight difficulty.
- I have a fair degree of difficulty in concentrating when I want to.
- L have a lot of difficulty in concentrating when I want to.
- I have a great deal of difficulty in concentrating when I want to.
- I cannot concentrate at all.

#### Section 7---- Work

- □ I can do as much as I want to.
- □ I can only do my usual work but no more.
- □ I can do most of my usual work, but no more.
- I cannot do my usual work
- □ I can hardly do any work at all.
- I can't do an work at all.

#### Section 8- Driving

- I can drive my car without any neck pain.
- I can drive my car as long as I want with slight pain in my neck.
- I can drive my car as long as I want with moderate pain in my neck.
- I can't drive my car as long as I want because of moderate pain in my neck.
- □ I can hardly drive at all because of severe pain in my neck.
- I can't drive my car at all.

#### Section 9 — Sleeping

- I have no trouble sleeping.
- □ My sleep is slightly disturbed (less than 1 hour sleep loss)
- □ My sleep is mildly disturbed (1-2 hour sleep loss).
- My sleep is moderately disturbed (2-3 hours sleep loss).
- □ My sleep is greatly disturbed (3-5 hours sleep loss).
- My sleep is completely disturbed (5-7 hours sleep loss).

#### Section 10— Recreation

- I am able to engage in all my recreational activities with no neck pain at all.
- I am able to engage in all my recreational activities with some pain in my neck.
- I am able to engage in most but not all of my usual recreational activities because of pain in my neck.
- I am able to engage in a few of my usual recreational activities because of pain in my neck.
- I can hardly do any recreational activities because of pain in my neck.
- I can't do any recreational activities at all.

Adapted from Vernon H, Mior S. The Neck Disability Index: A Study of Reliability and Validity. Journal of Manipulative and Physiological Therapeutics. 1991; 14(7):409-415.

#### APPENDIX B: NUMERIC PAIN RATING SCALE (NPRS) AND PAIN DIAGRAM

#### 2. Numeric Pain Rating Scale and Pain Diagram

Subject ID: \_\_\_\_\_

Date: / /

Please use the diagram below to indicate the symptoms you have experienced over the past 24 hours. **Be VERY precise when drawing the location of your pain.** Use the key to indicate the type of symptoms you have experienced.

Please rate your current level of pain on the following scale (circle ONLY one):

0 (no pain)		1	2	3	4	5	6	7	8	9 (worst imag	10 ginable pain)
Please rat	te your	worst l	evel of l	oain in tl	ne last 24	4 hours o	on the fo	llowing	scale (	circle ON	LY one):
0 (no pain)		1	2	3	4	5	6	7	8	9 (worst imag	10 ginable pain)
Please rate your best level of pain in the last 24 hours on the following scale (circle ONLY one):											
0 (no pain)		1	2	3	4	5	6	7	8	9 (worst imag	10 ginable pain)

Please direct questions to [name] at [contact] or [name]\[contact]

C: APPENDIX MODIFIED FEAR-AVOIDANCE BELIEFS (FABQ) QUESTIONNAIRE

Version: (2) 2/4/2025

